5.3 Definition of Dose-Limiting Toxicity

Dose limiting toxicity (DLT) will be defined as any non-hematologic toxicity of grade 3 or greater severity (excluding asymptomatic grade 3 laboratory abnormalities that are not life-threatening and respond to treatment; grade 3 fatigue; grade 3 nausea, vomiting or diarrhea occurring without optimal prophylaxis). Infectious toxicities will only be considered dose-limiting if grade 4 or greater. Any grade 4 non-hematological toxicity, as well as any irreversible grade 2 cardiac, renal or neurologic toxicities, will be considered dose-limiting. Grading of non-hematologic toxicities will be according to CTEP Active Version of the NCI Common Terminology Criteria for Adverse Events (CTCAE). DLT refers to toxicities experienced during the first cycle of treatment only.

Hematologic toxicity will be graded according to the 2008 IWCLL criteria (see table in section 6.3.1 under dose modifications)¹⁹. Hematologic toxicity will only be considered dose-limiting as follows:

Grade 4 neutropenia persisting for at least 7 days after discontinuation of study drug in Cycle 1 only. Neutropenia will not be considered a DLT for subjects with T-LGL.

Grade 4 thrombocytopenia persisting for at least 7 days after discontinuation of drug in Cycle 1 only.

Abnormal hematologic values are not noted as inclusion or exclusion criteria. Subjects with starting ANC \leq 1000 (or greater than 1000 but requiring growth factor support) or starting platelet count \leq 20,000 will not be evaluable for hematologic toxicity or hematologic DLT, as per consensus recommendations for clinical trials in CLL and T-LGL. Determination of whether to hold pyrimethamine for hematologic toxicities will be determined in these patients on a case by case basis by the treating physician and the Principal Investigator. As in Section 5.4 following, growth factor support and/or platelet transfusion are allowed at the investigator's discretion.

Dose-limiting toxicities will be determined during the 1st 28-day cycle only. There are no DLT parameters post Cycle 1.

Management and dose modifications associated with the above adverse events are outlined in Section 6 (Expected Toxicities and Dosing Delays/Dose Modifications).

Dose escalation will proceed within each cohort according to the following scheme.

Number of Participants with DLT at a Given Dose Level	Escalation Decision Rule
0 out of 3	Enter 3 participants at the next dose level.
≥ 2	Dose escalation will be stopped. This dose level will be declared the maximally administered dose (highest dose administered). Three (3) additional participants will be entered at the next lowest dose level if only 3 participants were treated previously at that dose.
1 out of 3	Enter at least 3 more participants at this dose level. 
 • If 0 of these 3 participants experience DLT, proceed to the next dose level. • If 1 or more of this group suffer DLT, then dose escalation is stopped, and this dose is declared the maximally administered dose. Three (3) additional participants will be entered at the next lowest dose level if only 3 participants were treated previously at that dose.
≤ 1 out of 6 at highest dose level below the maximally administered dose	This is generally the recommended Phase II dose. At least 6 participants must be entered at the recommended Phase II dose.

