6.3.1 Hematologic Toxicity

Hematologic toxicity will be graded according to IWCLL 2008 criteria¹⁹, as enumerated in the table below.

ANC / μl	Toxicity Grade	Decrease in Plts from Pre-Tx Value (Use this correction if starting plt count < 100,000)
>= 2,000	0	0-10%
>= 1,500 - 2000	1	11-24%
>= 1,000 – 1,500	2	25-49%

$\geq 500 - 1,000$	3	50-74%
< 500	4	$\geq 75\%$

Subjects will not be evaluable for hematologic toxicity, hematologic dose-limiting toxicity or holding of therapy based on low ANC if the starting ANC < 1000 or the starting ANC is greater than 1000 with the assistance of growth factors. The ANC may be supported by growth factors throughout study therapy for this group of patients. In particular, LGL patients with pre-existing neutropenia will not be evaluable for toxicity related to neutropenia and may continue study drug at their assigned dose regardless of neutrophil count.

Subjects with baseline platelets $< 20,000$ will not be evaluable for platelet toxicity. Subjects with baseline platelets $\geq 100,000$ will be evaluated per CTEP Active Version of the NCI Common Terminology Criteria for Adverse Events (CTCAE); i.e, do not use the correction in the table above for assessing platelet toxicity when baseline platelets $\geq 100,000$. When baseline and Cycle 1 Day 1 ANC and/or platelets differ, the lower of the two values should be used for assessing DLT, dose modifications and hematologic toxicity.

For subjects with initial ANC $\neq > 1000$, neutropenia grading will follow the table above and development of grade 4 neutropenia will result in temporary discontinuation of study drug. Consideration may be given to administration of folic acid, low-dose leucovorin or growth factors to these patients. Once recovery occurs subjects may be restarted at their previous dose. Those whose grade 4 ANC persists for at least 7 days despite these supportive care measures will be considered to have suffered dose limiting toxicity if this happens in the first cycle, only. If these subjects experiencing DLT are continued on study after resolution, they should undergo a one dose level reduction in dose. Although NOT considered a DLT in cycle 2 and beyond, if a subject experiences grade 4 ANC that persists for at least 7 days despite the supportive care measures listed above, the subject may undergo a one dose level reduction in dose at investigator discretion

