Thrombocytopenia will be graded based on the table above, using adjusted parameters for all subjects with a starting platelet count $< 100,000$. For those subjects with a starting platelet count $\neq > 100,000$, development of thrombocytopenia will be graded based on CTEP Active Version of the NCI Common Terminology Criteria for Adverse Events (CTCAE). Any subject with a starting platelet count $< 20,000$ will not be evaluable for hematologic toxicity, hematologic dose-limiting toxicity or holding of therapy based on thrombocytopenia. For any subject with a starting platelet count $> 20,000$, development of a platelet count $< 20,000$ is considered grade 4 thrombocytopenia and will result in holding of study drug. Consideration may be given to administration of folic acid or low-dose leucovorin. Persistence of grade 4 thrombocytopenia for > 7 days despite these supportive care measures will be considered a DLT if this happens in the first cycle. If these subjects experiencing DLT are continued on study after resolution within one month, a dose reduction by one dose

level per the dose escalation table is required. If grade 4 thrombocytopenia persists for > 7 days in cycle 2 or beyond, consideration may be given to a one dose level reduction, at the discretion of the Principal Investigator and treating investigator.

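### Sections 5.3 and 6.3.1 give opposite platelet DLT and drug-hold rules for patients who start neutropenic with platelets above 20,000

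*Combined protocol and SAP*

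**What the plan says.** **Section 5.3** names two triggers, and either is enough: a starting ANC of 1,000 or less (or above 1,000 only with growth factor), or starting platelets of 20,000 or less. Such subjects "will not be evaluable for hematologic toxicity or hematologic DLT, as per consensus recommendations for clinical trials in CLL and T-LGL". The wording covers all hematologic toxicity, not only the cell line that was low at the start. On stopping drug, it adds: "Determination of whether to hold pyrimethamine for hematologic toxicities will be determined in these patients on a case by case basis", with the decision shared by the treating physician and the Principal Investigator.

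**Section 6.3.1** works by cell line. Low starting ANC exempts a subject from rules based on low ANC, and the T-LGL example there mentions neutropenia only. Subjects with baseline platelets below 20,000 "will not be evaluable for platelet toxicity". For any subject who starts above 20,000, a fall below that value "is considered grade 4 thrombocytopenia and will result in holding of study drug". Then: "Persistence of grade 4 thrombocytopenia for > 7 days despite these supportive care measures will be considered a DLT", if it happens in the first cycle. The consequence follows: "If these subjects experiencing DLT are continued on study after resolution within one month, a dose reduction by one dose" level is required.

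**Who can be affected.** Section 5.3 states: "Abnormal hematologic values are not noted as inclusion or exclusion criteria". In Section 3.1, two of the six listed reasons to treat T-LGL are an ANC below 500, and an ANC below 1,000 with recurrent infections. Section 6.3.1 widens the group further: "When baseline and Cycle 1 Day 1 ANC and/or platelets differ, the lower of the two values should be used for assessing DLT".

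**The concern.** The 3+3 rule acts on the number of DLTs among three or six patients, so each event needs one unambiguous classification. Here a prolonged grade 4 platelet event in a patient who began neutropenic is counted under one section and ignored under the other. The same patient must stop drug under one section and may continue by discretion under the other, with platelets below 20,000.

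Cohorts 4 and 5 (100 and 150 mg) are still to be decided. They are two and three times the 50 mg dose already studied, and Section 2.1 gives possible myelosuppression as a reason for having a Phase I part at all. Section 14.2.1 expects only 2 to 12 further Phase I patients, so a single classification can matter.

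**Working it through.** This is a comparison of text. The escalation table in Section 14.2.1 is not in dispute. It follows from the stated rule, (1−p)³ + 3p(1−p)² × (1−p)³, to within one percentage point, but it uses one DLT rate p for everyone and cannot show this conflict.

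**Step 1: one patient under both rules.** Take starting ANC 400 and platelets 150,000. In Cycle 1 platelets fall to 10,000 and are still below 20,000 ten days after drug is stopped, despite supportive care. Ten days satisfies both the at-least-7-day limit in 5.3 and the more-than-7-day limit in 6.3.1, so the small difference in duration plays no part.

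| Question | Section 5.3 | Section 6.3.1 |
|---|---|---|
| Evaluable for platelet DLT? | No, because ANC is 1,000 or less | Yes, because platelets started above 20,000 |
| DLT? | No | Yes |
| Hold drug? | Case by case | Mandatory |
| Dose if continued | No DLT, so no DLT-driven reduction | One level lower, required |

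**Step 2: the mirror case.** Take a CLL/SLL patient with starting platelets below 20,000 and an ANC well above 1,000 without growth factor, who then has grade 4 neutropenia for at least 7 days in Cycle 1 despite supportive care. Section 5.3 makes the patient non-evaluable for any hematologic DLT because of the platelets. The ANC paragraph of 6.3.1 stops the drug, calls the event a DLT and asks for a one-level reduction if the patient continues.

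**Step 3: can 6.3.1 be read to agree with 5.3?** Its ANC sentence could be parsed so that the limitation to low ANC attaches only to holding therapy, leaving low-ANC subjects non-evaluable for every hematologic DLT. But the platelet paragraph would still apply its hold and its DLT to any subject starting above 20,000, so 6.3.1 would then contradict itself. The T-LGL sentence confined to neutropenia, and the separate platelet exemption, also favor the by-lineage reading.

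**Step 4: does the protocol say which section prevails?** No. Section 5.3 sends the reader to Section 6 for management and dose modification, Section 5.1.2 sends the reader to 6.3.1 for hematologic toxicity, and the nursing education sheet sends staff to 5.3 for it. The statement in 5.3 that neutropenia is not a DLT in T-LGL does not reach platelets.

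**Step 5: effect on the 3+3 decision of counting one such event.**

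| Count under 5.3 | Decision | Count under 6.3.1 | Decision |
|---|---|---|---|
| 0/3 | Next dose level | 1/3 | Three more patients at this dose |
| 1/3 | Three more patients | 2/3 | Stop |
| 1/6 | Next dose level | 2/6 | Stop; this is the maximally administered dose |

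The left-hand counts assume that the non-evaluable patient stays in the denominator. Section 14.2.1 counts the first three patients and gives no replacement rule. If such a patient were replaced, the platelet event would still go uncounted.

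**The case against.** The best reply is that 5.3 governs. Its title is the DLT definition, it says hematologic toxicity is dose-limiting only as it then lists, and its carve-out can be read as a specific exception to the general platelet rule in 6.3.1. This is the likelier reading for the DLT count. But 6.3.1 contains no such exception and nothing sets the precedence. Even if 5.3 settles the count, the mandatory hold in 6.3.1 and the case-by-case hold in 5.3 still disagree.

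A second reply is that the event would not vanish, and this is right. Everyone who takes one dose is evaluable for toxicity (14.6.1). Grade 4 hematologic events are excluded from SAE reporting only after the first cycle (11.5.1). The DSMC reviews toxicity (12.2). The Phase 2 dose rests on PK, PD and safety data together (Section 5). Unacceptable adverse events end therapy (5.5), and two physicians share the hold decision (5.3). A reader might infer that such patients would be unprotected; the documents do not support that. These safeguards mitigate the conflict, but they replace neither the DLT count nor a mandatory hold.

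A reader might also want to state how far the conflict shifts the escalation probabilities in 14.2.1. The documents do not support a figure. They give neither the frequency of low-ANC patients nor the share of DLT risk due to platelets. Such a patient is also exempt from neutropenia DLT under both sections, so the table's common rate would fit that patient under 6.3.1 only if neutropenia added nothing to DLT risk.

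Finally, 5.3 attributes its broad rule to consensus recommendations that are not in these documents. Choosing between a broad and a by-lineage rule is therefore partly the sponsor's judgment. Making the two sections agree is not.

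**Conclusion.** The inconsistency is real and narrow, and should be corrected before cohorts 4 and 5. It rests on the wording alone: two rules for the same event give opposite results on DLT status and on stopping drug, in patients whom the T-LGL criteria expressly admit. Its size is one step in a 3+3 decision for each affected patient, including the step from escalating to stopping.

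Frequency is unknown. A reader might infer that prolonged grade 4 thrombocytopenia is to be expected at 100 or 150 mg. Section 6.1.1 lists thrombocytopenia at higher doses without grade or duration, and Section 1.1 reports no clear drug-related toxicity so far, so that risk is neither shown nor excluded.

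**What to change.** State the DLT and evaluability rule once, in 5.3, and have 6.3.1 refer to it.

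- **Preferred:** make it lineage-specific, as 6.3.1 already does. Low starting ANC or growth-factor support would exempt a patient only from the neutropenia DLT and hold; low starting platelets would exempt only from the thrombocytopenia DLT and hold. The platelet DLT and mandatory hold would then apply to neutropenic patients who start above 20,000.
- **If the sponsor keeps the broad 5.3 rule:** write that exception into both the platelet and ANC paragraphs of 6.3.1, and state in 14.2.1 whether non-evaluable patients are replaced.
- **In the same edit:** use one duration and one set of cut-offs. Section 5.3 has 1,000 or less and 20,000 or less where 6.3.1 has below 1,000 and below 20,000. Repeat the T-LGL neutropenia exemption in the 6.3.1 ANC paragraph.

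The cost is a protocol amendment with IRB approval (Section 13.1) and a check that no event in completed cohorts 1 to 3 would be reclassified. No visits or tests are added, and no patients unless the sponsor chooses replacement.

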5.4 General Concomitant Medication and Supportive Care Guidelines

Patients will receive the following additional supportive care medications:

- Allopurinol 300 mg po QD day 1-10 after initiation of study therapy. This would be considered standard of care, unless the subject has an allergy. Subjects with T-LGL are not required to receive allopurinol.
- Anti-emetics may be prescribed as needed; no specific premedication is required or suggested.
- Subjects who have been taking trimethoprim-sulfamethoxazole for PCP prophylaxis should be assessed for their real risk of PCP. Due to an increased risk of hypersensitivity reactions and/or myelosuppression when given together with

pyrimethamine, this medication should be discontinued if possible or changed to atovaquone or other equivalent PCP prophylaxis during the time on study therapy.

- Subjects receiving acyclovir or equivalent prophylaxis should continue these medications. Consideration should be given to initiating acyclovir prophylaxis at 400 mg po TID (or equivalent) for those patients not yet receiving it.
- Lorazepam given concurrently with pyrimethamine has been associated with an increased risk of transaminitis. If substitution with another benzodiazepine or other medication is possible, then that is preferred; otherwise close monitoring is appropriate.
- All patients requiring transfusions should receive irradiated, leukopore filtered blood products.
- Subjects may receive neupogen, pegfilgrastim, erythropoietin or related growth factors at the discretion of the treating physician. Subjects in whom study therapy has been held due to myelosuppression may be given a short course of leucovorin 10 mg po QD, at the discretion of the treating physician in consultation with the Principal Investigator.
- Because there is a potential for interaction of pyrimethamine with other concomitantly administered drugs, especially sulfonamides or myelosuppressive drugs, the case report form must capture the concurrent use of all other drugs, over-the-counter medications, or alternative therapies.

5.5 Duration of Therapy

Initial response assessment will occur after 28 days of study therapy. Those subjects with stable or responding disease may continue on study indefinitely if their treating physician and the Principal Investigator feel that they are deriving clinical benefit. Subjects with significant adverse events or progressive disease should be removed from study.

Duration of therapy will depend on individual response, evidence of disease progression and tolerance. In the absence of significant adverse events, treatment may continue indefinitely or until one of the following criteria applies:

- Disease progression,
- Intercurrent illness that prevents further administration of treatment,
- Unacceptable adverse event(s),
- Participant decides to withdraw from the study, or

- General or specific changes in the participant's condition or compliance render the participant unacceptable for further treatment in the opinion of the treating investigator.

5.6 Duration of Follow Up

Participants will be followed until initiation of their next therapy or until death, whichever occurs first. Their general medical condition and survival status will be followed for the duration of their life, even after additional therapies. Subjects not presenting in clinic on a regular basis may be called by the study staff when possible. Participants removed from study for unacceptable adverse events will be followed until resolution or stabilization of the adverse event.

5.7 Criteria for Removal from Study

Participants will be removed from study when any of the criteria listed in Section 5.5 apply. The reason for study removal and the date the participant was removed must be documented in the study-specific case report form (CRF). Alternative care options will be discussed with the participant.

In the event of unusual or life-threatening complications, participating investigators must immediately notify the Principal Investigator (or Protocol Chair), [name] at [contact].

6. EXPECTED TOXICITIES AND DOSING DELAYS/DOSE MODIFICATIONS

Dose delays and modifications will be made using the following recommendations, and as per Table 2, Section 6.3. Toxicity assessments for non-hematologic toxicities will be done using CTEP Active Version of the NCI Common Terminology Criteria for Adverse Events (CTCAE) which is identified and located on the CTEP website at: http://ctep.cancer.gov/protocol_Development/electronic_applications/ctc.htm. Please see below for appropriate evaluation of hematologic toxicities, which will be according to the IW-CLL 2008 criteria.

If possible, symptoms should be managed symptomatically. In the case of toxicity, appropriate medical treatment should be used (including anti-emetics, anti-diarrheals, etc.).

All adverse events experienced by participants will be collected from the time of the first dose of study treatment, through the study and until the final study visit. Participants continuing to experience toxicity at the off study visit may be contacted for additional assessments until the toxicity has resolved or is deemed irreversible.

6.1 Anticipated Toxicities

A list of the adverse events and potential risks associated with the agents administered in this study appear below and will determine whether dose delays and modifications will be made or whether the event requires expedited reporting **in addition** to routine reporting.

6.1.1 Adverse Event Lists(s) for Pyrimethamine

Hypersensitivity reactions, occasionally severe (such as Stevens-Johnson syndrome, toxic epidermal necrolysis, erythema multiforme, and anaphylaxis), and hyperphenylalaninemia, can occur particularly when **pyrimethamine** is administered concomitantly with a sulfonamide. Anorexia and vomiting may occur. Vomiting may be minimized by giving the medication with meals; it usually disappears promptly upon reduction of dosage. Higher doses may produce megaloblastic anemia, leukopenia, thrombocytopenia, pancytopenia, atrophic glossitis, hematuria, and disorders of cardiac rhythm. Hematologic effects, however, may also occur at low doses in certain individuals. Pulmonary eosinophilia has been reported rarely.

6.2 Toxicity Management

Following the ingestion of 300 mg or more of **pyrimethamine**, gastrointestinal and/or central nervous system signs may be present, including convulsions. The initial symptoms are usually gastrointestinal and may include abdominal pain, nausea, severe and repeated vomiting, possibly including hematemesis. Central nervous system toxicity may be manifest by initial excitability, generalized and prolonged convulsions which may be followed by respiratory depression, circulatory collapse, and death within a few hours. Neurological symptoms appear rapidly (30 minutes to 2 hours after drug ingestion), suggesting that in gross overdose pyrimethamine has a direct toxic effect on the central nervous system. The fatal dose is variable, with the smallest reported fatal single dose being 375 mg. There are, however, reports of pediatric patients who have recovered after taking 375 to 625 mg.

There is no specific antidote to acute pyrimethamine poisoning. In the event of overdose, symptomatic and supportive measures should be employed. Gastric lavage is recommended and is effective if carried out very soon after drug ingestion. Parenteral diazepam may be used to control convulsions. Folinic acid should also be administered within 2 hours of drug ingestion to be most effective in counteracting the effects on the hematopoietic system. Due to the long half-life of pyrimethamine, daily monitoring of peripheral blood counts is recommended for up to several weeks after the overdose until normal hematologic values are restored.

